3.7 Procedures related to neutropenia

During the two phase 1 trials with 1790GAHB, two subjects of African descent experienced a transient and clinically asymptomatic decrease of circulating neutrophils of

grade 3 (severe) that was finally classified as "benign ethnic neutropenia". In addition, six more subjects experienced transient and clinically asymptomatic grade 2 (moderate) neutropenia. Although this finding was not associated with any clinical illness, some precautionary procedures for enrollment and monitoring of trial subjects were introduced to protect the safety of study subjects, including selection of subjects with baseline ANC above $1.8 \times 10^9/L$.

In order to maintain a prudent approach, but, at the same time, to not compromise the scientific validity of the clinical trial by selecting participants that are not entirely representative of the local healthy population (if non-local laboratory reference intervals are used) a step-wise approach will be adopted for the present trial H03_04TP. More specifically, same as in Phase 1 trials, the more conservative western normal ranges will be adopted for ANC collected up to 7 days after 1st vaccination of the initial 18 subjects.

Subsequently, all safety data from these 18 subjects will be evaluated by the DSMB which will make a recommendation as to whether the enrollment and assessment of neutropenia during the study of further subjects could be done using the local normal ranges published for neutrophils (Karita et al., 2009) and for which a consensus interval of 1.0 to $5.3 \times 10^9/L$ has been reached, or should be continued using the western normal ranges adopted for the first 18 subjects. This is also in consideration of the clinically benign nature of the events reported in the phase 1 studies and of the documented lower absolute neutrophils counts in healthy African populations (one of the key targets for this vaccine) compared to western populations (Badenhorst et al., 1995, Ezeilo, 1972, Lugada et al., 2004),

Therefore, study procedures will be as follows:

- First subset of 18 subjects (prior to DSMB evaluation of data):

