Subjects with ANC less than $1.8 \times 10^9/L$ at screening will not be enrolled in the study. All individuals with ANC $< 1.8 \times 10^9/L$, occurring at 7 days after the first dose, will have additional blood draws for complete blood count to be repeated on a weekly basis until the neutropenia resolves ($ANC \geq 1.8 \times 10^9/L$). In case the ANC is less than $0.5 \times 10^9/L$ after 1st vaccination, the subject will be immediately discontinued from 2nd vaccination and will have the test repeated on a weekly basis until the neutropenia resolves.

- All subjects (after DSMB evaluation of safety data from the initial 18 subjects with recommendation to switch to local normal ranges published for neutrophils):

Subjects with neutropenia defined as ANC less than $1.0 \times 10^9/L$ at screening will not be enrolled in the study. All individuals with a neutropenia ($ANC < 1.0 \times 10^9/L$), occurring

at any time during the study 7 days after the first dose, will have additional blood draws for complete blood count to be repeated on a weekly basis until the neutropenia resolves ($ANC \geq 1.0 \times 10^9/L$). In case the ANC is less than $0.5 \times 10^9/L$ after 1st vaccination, the subject will be immediately discontinued from 2nd vaccination and will have the test repeated on a weekly basis until the neutropenia resolves.

For classification and grading of severity of neutropenia for the first subset of 18 subjects, the criteria of Common Terminology Criteria for Adverse Events (CTCAE) issued by US Department of Health and Human Services (version 4.3; 2010) will be adopted. In case DSMB endorses the use of local ranges of normality for the second subset of 54 subjects, the grading will be modified based on input from DSMB. All individuals with neutropenia either ongoing or with onset at visit 5 (or last study visit) will have additional blood draws for complete blood count to be repeated on a regular basis until the neutropenia resolves ($ANC \geq 1.0 \times 10^9/L$ or $ANC \geq 1.8 \times 10^9/L$, depending on recommendations given by DSMB after evaluation of safety data from the initial 18 subjects).

Finally, all cases of neutropenia, regardless of intensity, will be considered as Adverse Events of Special Interest (AESI) from a reporting perspective.

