7.1.4.1 Adverse Events of Special Interest

Adverse events of special interest (AESIs) are predefined adverse events that will be specifically highlighted to the investigator and will be summarized separately at the end of the study. All AESIs occurring during the study will be categorized and reported as a SAE.

Reactive arthritis (ReA) will be collected and analyzed as an AESI for this study.

Reactive arthritis is defined as non-purulent joint inflammation that develops in response to an infection in another part of the body. Since the inflammation is triggered by a previous condition, it is termed “reactive”. Intestinal pathogens that have been associated with reactive arthritis include *Campylobacter*, *Salmonella*, *Yersinia*, *Clostridium difficile*, and *Shigella*. If reactive arthritis is caused by an auto immune response, there is at least a possibility that it could be initiated by vaccination of susceptible people with the 1790GAHB vaccine.

For diagnosis of ReA, imaging and aspiration are not required (unless clinically indicated).

Neutropenia, a decrease of circulating neutrophils below the lower limit of the range of normality, will be collected and analyzed as an AESI for this study. To this purpose, as specified in the study procedures, subjects in this trial will have multiple blood draws for monitoring potential episodes of post vaccination neutropenia. For additional information on neutropenia, please refer to Section 3.7, Procedures Related To Neutropenia

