8. STATISTICAL CONSIDERATIONS

8.1 Endpoints

8.1.1 Primary Endpoint(s)

8.1.1.1 Primary Safety Endpoint(s)

The safety profile of the two vaccine doses and control(s) will be assessed through measurement of the following:

- a. Number and percentage of subjects with solicited local and systemic adverse reactions during 7 days following each vaccination.
- b. Numbers and percentage of subjects with deviations from normal ranges of safety laboratory data after each vaccination.
- c. Number and percentage of subjects with reported unsolicited adverse events during 28 days following each vaccination.
- d. Number and percentage of subjects with reported SAEs throughout the study duration.
- e. Number and percentage of subjects with reported reactive arthritis or neutropenia (AESIs).

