13.3 Unsolicited Adverse Events

All AEs occurring during the first 28 days after each vaccination, including the day of vaccination, and all AEs leading to withdrawal, all SAEs and all AEs of special interest occurring at any time during the study will be recorded according to the protocol-specified reporting rules.

The original verbatim terms used by investigators to identify adverse events in the CRFs will be mapped to preferred terms using the MedDRA dictionary. The unsolicited adverse events will then be grouped by MedDRA preferred terms into frequency tables according to system organ class. Adverse events judged by the investigator as at least possibly related to study vaccine will be summarized by vaccine group, according to system organ class and preferred term within system organ class. When an unsolicited adverse event occurs more than once for a subject, the maximal severity and strongest relationship to the vaccine group will be counted.

Only vaccine-emergent adverse events (see [section 8.7](#) for definition) will be analyzed, i.e., excluding those after a subject has given informed consent but before vaccination. The selection of unsolicited adverse events and the assignment to time intervals will be done by day of onset and not by days ongoing/persisting.

The summaries will be presented by period of onset and will include frequency distributions of the different adverse events:

- Onset between day 1 and study termination.

The analysis of unsolicited adverse events comprises the following categories:

- Any unsolicited adverse event.
- Possibly or probably related unsolicited adverse events.
- Unsolicited adverse events leading to death.
- Serious adverse events.
- Possibly or probably related serious adverse event.
- Unsolicited adverse events leading to premature withdrawal from study.

- Unsolicited adverse events leading to dose reduction, interruption or delay in study vaccination.
- Unsolicited adverse events leading to hospitalization.

Solicited adverse events continuing beyond day 7 will be coded by MedDRA and combined with the respective unsolicited adverse events.

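### If the DSMB adopts local ranges, primary endpoint (e) pools neutropenia judged at ANC <1.8 with neutropenia judged at ANC <1.0, so its rate belongs to neither limit

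*Protocol*

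**What the plan says.** Protocol 8.1.1.1 lists as primary safety endpoint (e): "Number and percentage of subjects with reported reactive arthritis or neutropenia (AESIs". Protocol 7.1.4.1 defines the event without a number, "Neutropenia, a decrease of circulating neutrophils below the lower limit of the range of normality", and refers to 3.7. Section 3.7 adds that neutropenia of any intensity is reported as an AESI.

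Section 3.7 sets the limit in steps:

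- **Start of the trial.** "western normal ranges will be adopted for ANC collected up to 7 days after 1st vaccination of the initial 18 subjects". The bullet for this stage uses ANC <1.8 x 10^9/L, both to exclude at screening and to trigger repeat counts at 7 days after dose 1.
- **After a DSMB recommendation to switch.** The next bullet is headed "All subjects (after DSMB evaluation of safety data from the initial 18 subjects with recommendation to switch to local normal ranges published for neutrophils" and uses ANC <1.0.
- **Question put to the DSMB.** Whether "assessment of neutropenia during the study of further subjects could be done using the local normal ranges".
- **Grading.** CTCAE is used "For classification and grading of severity of neutropenia for the first subset of 18 subjects". "In case DSMB endorses the use of local ranges of normality for the second subset of 54 subjects", the grading is to be modified on DSMB advice.
- **Visit 5.** Follow-up continues until ANC reaches 1.0 or 1.8, according to what the DSMB recommended. Cohort is not mentioned.

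SAP 13.3 sets no limit of its own: "all AEs of special interest occurring at any time during the study will be recorded according to the protocol-specified reporting rules". SAP 13.5 plans 3 x 3 shift tables by arm and time point. SAP 8.8 takes their reference ranges from the site laboratory and gives no values. Both documents mark subgroups as not applicable.

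**The concern.** After a switch, the same count can be an endpoint event in one subject and not in another. An ANC of 1.5 at Visit 2 is neutropenia in subject 10 and normal in subject 30. Endpoint (e) adds the two cohorts together, and nothing in the SAP re-scores the first 18, reports them separately or names one limit for analysis.

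Neutropenia is the laboratory signal carried over from phase 1, where 3.7 reports two grade 3 and six grade 2 cases. In a descriptive trial the reported rates are the result. A rate that mixes two limits is hard to interpret and cannot be set beside a rate from a trial that used one limit.

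A smaller issue is that 3.7 is not fully clear about which limit the first 18 carry at Visits 3 to 5 once a switch has been made.

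**Working it through.** **Does the pooling follow from the text?** The limits applied after a switch are:

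| Subjects | Visit 2 | Visits 3-5 |
|---|---|---|
| First 18 | <1.8 | <1.0 (better supported) or <1.8 |
| Other 54 | <1.0 | <1.0 |

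The Visit 2 column is mixed under either entry in the last column, so the pooling does not depend on settling the ambiguity. Without a switch, all 72 are judged at 1.8 and neither problem arises.

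**Which limit do the first 18 carry later?** Three texts support 1.0: the two bullets are divided by time (before and after DSMB evaluation), the western range stops at 7 days after dose 1, and the Visit 5 sentence follows the DSMB recommendation rather than the cohort. Two texts point to 1.8: the reference to further subjects in the question to the DSMB, and the grading text that separates 18 from 54. The balance favours 1.0, with some doubt left.

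**The plan's own figure.** The documents give no expected neutropenia rate. The synopsis figure of 87% for at least one event in 20 subjects at a 10% rate reproduces as 1 - 0.9^20 = 0.878, and this point does not affect it.

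**Illustrative size.** The inputs from the documents are 18 and 54 subjects, limits of 1.8 and 1.0, and the local interval 1.0 to 5.3. The following are assumed: ANC is log-normal with that interval as its 95% range, within-subject CV is 15-30%, every count below the limit is reported, there is no dropout, and the vaccine has no effect.

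- Log mean = (ln 1.0 + ln 5.3)/2 = 0.834. Log SD = (ln 5.3 - ln 1.0)/(2 x 1.96) = 0.425, covering variation between and within subjects.
- The first 18 are conditional on screening ANC >=1.8, and the later 54 on >=1.0.
- Expected count in (e) = 18 x P(case, first cohort) + 54 x P(case, later cohort), by simulation with 1.5 million draws per setting.

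| Expected subjects | CV 15% | CV 30% |
|---|---|---|
| First 18, with 1.0 at Visits 3-5 | 1.69 | 3.54 |
| Later 54 | 1.61 | 3.57 |
| Endpoint (e), all 72 | 3.3 | 7.1 |
| First-18 share of cases | 51% | 50% |
| All 72 at a fixed 1.0 | 1.6 | 4.1 |
| All 72 at a fixed 1.8 | 25.1 | 37.5 |

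The share at CV 15% is 1.69/(1.69 + 1.61) = 51%, against 18/72 = 25% of subjects. If 1.8 applied to the first 18 throughout, the totals would be 5.3 and 11.6, with a share of about 70%.

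**Caution on the fixed-1.8 row.** Under the same model about 14 of the later 54 enter with ANC between 1.0 and 1.8. They supply 13.1 of the 25.1 cases and 11.9 of the 37.5. Without them the row is 25.1 - 13.1 = 12.0 and 37.5 - 11.9 = 25.6.

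**Between arms.** With an assumed 30% fall at Visits 2 and 4 in both vaccine arms and 6 of the first 18 in each arm, vaccine minus control is 18.2 points with 1.0 at Visits 3-5 and 18.0 with 1.8 (CV 15%), or 19.1 and 17.7 (CV 30%). The choice of reading hardly moves it.

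**The case against.** The strongest reply is that the two limits are deliberate. Section 3.7 explains a stepwise approach that weighs caution against recruiting subjects who represent the local population. It operates only if the DSMB switches, and the DSMB Charter, which is not among the documents, may settle how the first 18 are handled. That is a good defence of the design for enrolment and monitoring. It does not explain why the analysis should add the two cohorts together without a count at a common limit.

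Much is also recoverable. SAP 13.5 summarises laboratory values by arm and time point and flags out-of-range values in listings, and Protocol 8.4.2.1.3 requires a separate AESI summary. A reader could recount 72 subjects by hand. This stands, and it makes the missing table a matter of presentation rather than of lost data.

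Three stronger readings are tempting and should not be adopted:

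- **That 3.7 contradicts itself outright.** Most of its text points to 1.0 for the first 18 after the switch, so ambiguity is the fair word.
- **That the shift tables cannot give a count at either limit.** The site-laboratory limit is not stated, and if it were 1.0 or 1.8 they would give that count by visit. What can be said is that no any-visit count is planned and nothing specifies agreement with the AESI total.
- **That the vaccine-control comparison is biased.** Allocation is randomised with concurrent controls, and each limit applies alike in every arm.

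The holding rules in 3.6 use fixed limits of 0.5 and 1.0 and are unaffected.

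**Conclusion.** The point holds, conditional on a DSMB switch. Endpoint (e) would then be a two-limit mixture, and its absolute rate would not be the rate at ANC <1.8 or at ANC <1.0. The between-arm comparison is not biased, although the size of the difference also reflects a mixture of limits. The ambiguity in 3.7 is secondary, and resolving it would not cure the pooling.

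The sizes are illustrative only, because they rest on an assumed ANC distribution and within-subject CV. On those assumptions, with no vaccine effect and 1.0 applied to the first 18 after the switch, a quarter of the subjects supply about half of the cases. Endpoint (e) is then expected to count 3.3 to 7.1 subjects, against 1.6 to 4.1 at a fixed 1.0. The much larger fixed-1.8 counts should not be read as the number of new cases missed, because a third to a half of them come from subjects who entered below 1.8 (11.9/37.5 = 32%; 13.1/25.1 = 52%). The change is worth making because the endpoint is primary and the remedy is cheap.

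**What to change.** **SAP 13.5.** Beside the reported AESIs, tabulate for all 72 subjects, by arm, at each of Visits 2 to 5 and at any post-vaccination visit, the number and percentage with ANC <1.0 and with ANC <1.8. Split the <1.8 count by screening ANC (>=1.8 versus 1.0 to <1.8), so that low baseline values are not counted as new neutropenia.

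**Protocol 3.7.** Add one sentence naming the limit that applies to the first 18 subjects after a switch. A limit of 1.0 agrees with most of the existing text. This removes the ambiguity but not the pooling, so the table is still needed.

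**Cost.** One derived table from counts already scheduled, and one clarifying sentence. No further blood draws are needed, and the enrolment and holding rules do not change.

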3.8 Data Monitoring Committee

A DSMB will be in place to receive from GVGH a summary of all safety data (solicited local and systemic AEs, unsolicited AEs and SAEs) and listings of clinically significant modifications in hematology, blood chemistry and urine dipstick/ urinalysis test values obtained during one week follow-up post-first vaccination of the initial 18 subjects. Based on evaluation of the safety data, the DSMB will make a recommendation to GVGH, as to whether the enrollment can be completed or not. Additionally, DSMB will make a recommendation to GVGH, as to whether the enrollment of further subjects could be done using the published local normal ranges for neutrophils in Africa (Karita et al., 2009) or should instead be continued using the western normal ranges adopted for the first 18 subjects.

In addition to the evaluation of the safety data from the initial 18 subjects, DSMB will be consulted for any safety issue that might be reported during the trial.

The composition of DSMB and the details of all relevant procedures will be documented in the DSMB Charter.

3.9 Premature Withdrawal from Study

Subjects may withdraw at any time, or be dropped from the study at the discretion of the investigator should any untoward effects occur and/or for safety reasons. In addition, a

subject may be withdrawn by the investigator or the Sponsor if he/she violates the study plan or for administrative reasons. The investigator or study coordinator must notify the Sponsor immediately when a subject has been withdrawn due to an adverse event.

The circumstances above are referred to as premature withdrawal from the study, and the reason for premature withdrawal should be clearly documented and detailed in the source documentation. The investigator should make every attempt to evaluate the subject's safety, including resolution of ongoing AEs, at the time of premature withdrawal. If a subject wants to withdraw from the study before all doses are administered or prior to the last planned study visit, the subject will be asked to be followed for safety for the duration of the study. When a subject withdraws, or is withdrawn, from the study, the procedures described in [section 5.5.1, Early Termination Visit](#) should be completed if possible.

The reasons for premature withdrawal from the study include: Adverse event, death, withdrawal of consent, lost to follow-up, administrative reason, and protocol deviation. These reasons are described in greater detail below.

Adverse Event

For any subject withdrawn from study participation prior to the planned Study Termination Visit, it is important to determine if an AE was associated with the reason for discontinuing the study. This AE must be identified on the AE CRF page by indicating "Withdrawn from study due to AE". Any ongoing AEs at the time of study withdrawal must be followed until resolution or stabilization.

Subjects who develop a serious adverse event (SAE) judged to be possibly or probably related to the study vaccine, including hypersensitivity reactions, should not receive subsequent vaccination.

Death

For any subject withdrawn from study participation due to death, this should be noted on the Study Termination CRF page and the associated SAE that led to the death must be reported.

Withdrawal of consent

The subject can withdraw consent for participation in the study at any time without penalty or loss of benefit to which the subject is otherwise entitled. Reason for early termination should be deemed as "withdrawal of consent" if the subject withdraws from participation due to a non-medical reason (i.e., reason other than AE). If the subject intends to withdraw consent from the study, the investigator should clarify if the subject

will withdraw completely from the study or if the subject will continue study participation for safety, or a subset of other study procedures. If the subject requests complete withdrawal from the study, no further study interventions will be performed with the subject.

Lost to Follow-Up

For subjects who fail to show up for final visits (clinic or home visits), or for three consecutive visits, study staff are encouraged to make at least three documented attempts to contact the subject to encourage the completion of study termination procedures. These efforts to contact the subject should be recorded in the source document. The termination date for the subject to be captured on the Study Termination CRF page is the date of the last successful contact (clinic visit or home visits) with the subject.

Administrative Reason

Examples for subjects withdrawn from the study due to administrative reason can include: Sponsor decision to terminate the study, subject meeting a pre-specified withdrawal criterion, subject discontinuation for insurance issues, moving, no time, etc. This reason should be noted in the Study Termination CRF page and any ongoing AEs at the time of study withdrawal must be followed until resolution/stabilization.

If the clinical study is prematurely terminated by the Sponsor, the investigator is to promptly inform the study subjects and local EC/IRB and should assure appropriate therapy and follow up for the subjects. All procedures and requirements pertaining to the archiving of study documents should be followed. All other study materials (study medication/vaccines, etc.) must be returned to the Sponsor.

For subjects who are withdrawn from the study due to receipt of an excluded medication/vaccination or due to significant protocol non-compliance, this reason should be noted in the Study Termination CRF page.

In studies that involve more than 1 consecutive dose of study vaccine, a separate event is **“withdrawal of study vaccination”**. This event may occur if subjects are expected to receive more than 1 consecutive dose of vaccine as part of study participation. The act of withholding additional study vaccinations is referred to as withdrawal of study vaccination. Subjects may be withdrawn from study vaccination for several reasons including but not limited to: AE related to earlier vaccinations, failure to meet inclusion or exclusion criteria for revaccination (see [section 4.0, Selection Of Study Population](#)), or pregnancy. **Subjects who are withdrawn from study vaccination should be encouraged to continue in the study for safety follow-up and other procedures as appropriate until the scheduled termination visit.** If the subject is withdrawn from

study vaccination(s) due to adverse event, this event must be linked to the withdrawal from vaccination on the AE CRF page

Protocol Deviation

A protocol deviation is any change, divergence, or departure from the study design or procedures of a study protocol. In general, subjects associated with protocol deviations may remain in the study unless continuation in the study jeopardizes the subject's health, safety, or rights.

Investigators will apply due diligence to avoid protocol deviations. Under no circumstances should the investigator contact GVGH or its agents, if any, monitoring the study to request approval of a protocol deviation, as no authorized deviations are permitted. If the investigator feels a change to the protocol would improve the conduct of the study this must be considered a protocol amendment, and unless such an amendment is agreed upon by GVGH and approved by the IRB/EC and health authorities it cannot be implemented.

Any subject who becomes pregnant during the study, despite the protocol requirement for adequate contraception, will not receive further vaccination but should be encouraged to continue participating in the study for safety follow-up. The site must complete a paper Pregnancy Report CRF (initial report) as soon as possible after learning of pregnancy occurrence (see [section 7.1.6, Pregnancies](#) for further details). If the subject withdraws from the study for any of the above categories except death, the site will obtain permission from the subject to continue to remain in contact with her until the outcome of the pregnancy is known, even if the outcome is not known until after the subject reaches the end of follow-up period.

Refer to [section 3.6, Stopping/Pausing Guidelines](#) and to [section 3.7 Procedures related to neutropenia](#) for further details in case of neutropenia.

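### Section 3.9 does not ask a vaccinated subject removed from the study by the investigator or sponsor to complete safety follow-up, so later safety data can be lost for a reason linked to the primary outcome

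*Protocol*

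**What the plan says.** All references are to the current protocol (version 4.0) and the SAP.

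**Removal from the study.** Protocol 3.9 allows a subject to "be dropped from the study at the discretion of the investigator should any untoward effects occur and/or for safety reasons". It sets no threshold of severity or relatedness. It adds that a "subject may be withdrawn by the investigator or the Sponsor if he/she violates the study plan or for administrative reasons".

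**Who is asked to stay.** The request for full-duration follow-up is conditional: "If a subject wants to withdraw from the study before all doses are administered or prior to the last planned study visit", then "the subject will be asked to be followed for safety for the duration of the study". Later in 3.9, for the separate event of stopping vaccination only, "Subjects who are withdrawn from study vaccination should be encouraged to continue in the study for safety follow-up". A subject who becomes pregnant is likewise encouraged to continue. On deviations, 3.9 says that, in general, "subjects associated with protocol deviations may remain in the study unless continuation in the study jeopardizes" the subject's health, safety or rights.

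**What is still captured after removal.** The early termination visit covers both routes: "When a subject withdraws, or is withdrawn, from the study, the procedures described in" section 5.5.1 are to be completed if possible. These include an AE interview and safety bloods. Also, "Any ongoing AEs at the time of study withdrawal must be followed until resolution or stabilization".

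**What stops.** Protocol 7.1 closes AE observation at early termination if that comes first. Section 5.5.1 keeps laboratory results obtained after termination in the medical records only. Section 7.1.5.1 requires an SAE outside the follow-up period to be reported only if it is thought to be caused by the vaccine. SAP 6.1 does not treat assessments missed after premature termination as protocol deviations.

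**The concern.** Safety is the only primary objective. The endpoints in protocol 8.1.1.1 run over 7 and 28 days after each injection and, for SAEs, over the whole study. A rule that lets observation end because an adverse effect occurred ties missing safety data to the outcome being measured. If removals were more frequent in the more reactogenic arm, the comparison with control would be blurred in the reassuring direction.

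Neutropenia makes this concrete. It is an AESI and part of a primary endpoint, it is found by scheduled counts, and section 3.7 describes the phase 1 cases as clinically silent. A subject removed on day 3 for another reaction may have one count, at the early termination visit, instead of the counts planned at day 7 and later. Those counts also feed the study-hold rule in section 3.6.

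**Working it through.** **1. Routes out of the study, side by side**

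| Route | Asked to continue safety follow-up? |
|---|---|
| Subject wants to leave | Yes, for the study duration (3.9) |
| Vaccination stopped, study continues | Encouraged, to the termination visit (3.9) |
| Pregnancy | Encouraged (3.9) |
| Removed from the study by the investigator for an untoward effect | Not stated; early termination visit and ongoing AEs only |
| Removed from the study by the investigator or sponsor for a plan violation or administrative reason | Not stated; early termination visit and ongoing AEs only |

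The gap is in the last two rows. The second row is also unsettled. Section 5.5.1 applies early termination procedures to subjects withdrawn from treatment and says that completing the termination page ends participation, whereas 3.9 encourages them to continue.

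**2. How the SAP treats a removed subject**

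- *Unsolicited AEs, SAEs, AESIs.* SAP 7.5 keeps any exposed subject with AE data, and a confirmation of no AE counts as data. Length of follow-up plays no part. An event missed after removal lowers the numerator and leaves the denominator unchanged.
- *Solicited AEs.* SAP 13.2 drops a subject with no plausible observation in the interval, but one observation is enough to keep the subject. SAP 8.2.1 imputes nothing. Someone removed on day 2 therefore counts as observed through day 7 for each symptom with an observation.
- *Laboratory values.* SAP 13.5 uses subjects with available data. The problem here is informative missingness, not a retained denominator.

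**3. The plan's own figures** (synopsis: 24 per group, 15% drop-out, 20 evaluable, 10% event rate, 87%)

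- 20 / (1 − 0.15) = 23.5, rounded up to 24. Reproduced.
- P(at least one event) = 1 − 0.9^20 = 87.8%, against 87% stated. Reproduced.
- With all 24 followed: 1 − 0.9^24 = 92.0%.

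**4. Illustration of size**

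The documents give no number of removals. Assume that *m* of 24 in an arm are removed before a later event window, that overall true risk of the later event is 10%, and that removed subjects have *r* times the risk of the others.

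- Risk among those retained: b = 0.10 × 24 / (24 − m + m·r)
- Expected rate with 24 kept in the denominator: b × (24 − m) / 24
- P(at least one observed) = 1 − (1 − b)^(24 − m)

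| m | r | Risk in retained | Rate over 24 | P(at least one observed) |
|---|---|---|---|---|
| 1 | 1 | 10.0% | 9.6% | 91.1% |
| 1 | 3 | 9.2% | 8.8% | 89.2% |
| 2 | 1 | 10.0% | 9.2% | 90.2% |
| 2 | 3 | 8.6% | 7.9% | 86.1% |
| 4 | 1 | 10.0% | 8.3% | 87.8% |
| 4 | 3 | 7.5% | 6.25% | 79.0% |

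For example, with m = 4 and r = 3, b = 2.4 / 32 = 7.5%. The retained-risk column suits laboratory endpoints; the rate over 24 suits unsolicited AEs, SAEs and AESIs. One subject is 1/24 = 4.2 points.

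**The case against.** The protocol already limits the loss. The AE that led to withdrawal must be identified on the AE CRF page, ongoing AEs are followed, the early termination visit explicitly covers subjects who are withdrawn, and vaccine-caused SAEs stay reportable. AEs leading to withdrawal are summarized separately, so this attrition is visible. The specific rules act on vaccination rather than participation: a related SAE (3.9) and a very low neutrophil count (3.7) both stop the second injection. The endpoints also count subjects, so one removed for an unsolicited AE is already a case for any unsolicited AE.

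All of that stands, and it rules out several stronger readings:

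- *Safety data on removed subjects are lost wholesale.* They are not. The loss is confined to new events and scheduled assessments after removal.
- *Every safety rate is biased downward because removed subjects stay in the denominator.* The SAP does not keep them there for laboratory summaries, nor for solicited intervals with no data.
- *An arm's rate could be understated by 4/24 = 16.7 points.* That would need the whole drop-out allowance to be reaction-driven removals in one arm, each followed by a missed event not already counted. Nothing in the documents supports that combination.
- *Section 3.9 contradicts itself on deviations.* Both statements are permissive: one says withdrawal may happen, the other gives staying as the general position with an exception. They should be aligned, but they do not conflict.

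None of this supplies the missing request. Removal from the study remains open to the investigator for any untoward effect, and no passage asks that subject to complete the scheduled safety visits.

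**Conclusion.** The gap is real and bounded. Followed as written, the plan can lose new AEs, AESIs and scheduled safety bloods after an investigator or sponsor removal, for a reason connected with the primary outcome. The direction is downward for unsolicited AEs, SAEs and AESIs, and for solicited AEs when removal falls partway through the 7-day interval. For laboratory endpoints it is informative missingness.

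The size cannot be fixed from the documents, because removal is permitted rather than expected and no rate is given. Under the stated assumptions (10% overall risk, threefold risk in those removed), one removal takes expected risk among those retained to 9.2% and four take it to 7.5%. At equal risk, retained risk does not move and only the rate over 24 falls. In a descriptive two-month study this is a cheap improvement, not a flaw that undermines the design.

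**What to change.** 1. In protocol 3.9, extend the existing request for safety follow-up to the end of the study to every vaccinated subject withdrawn by the investigator or sponsor, where consent allows and the study continues.
2. In 7.1 and 5.5.1, state that AE and safety laboratory data from this follow-up are collected and entered in the eCRF.
3. Reconcile 3.9 with 5.5.1 on whether a subject withdrawn from vaccination stays in follow-up, and align the two statements in 3.9 on subjects with deviations.

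The cost is protocol wording and a few subjects completing visits already scheduled. No change is proposed to the investigator's discretion or to who receives the second injection.
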